7.4 Analysis Methods

For each body site, when per-protocol data are different from mITT data for \log_{10} CFU/cm², log reduction, or product expression volumes, per-protocol analysis and mITT analysis will be performed separately using the same statistical methods. The following analysis methods will be applied to both per-protocol analysis and mITT analysis, both abdomen and groin.

An alpha level of 5% (two-sided) is used for all analyses.

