7.4.2 Secondary Analysis

The ITT data set (all randomized subjects) will be considered evaluable for safety. Skin irritation scores will be reported for any subject who is scored with a 1 or more at any observation (baseline treatment day or the 10 minute post-application time point) in any category for any site.

Based on the protocol, subjects who receive an irritation score of 1 or greater (any redness, swelling, rash, or dryness present at any treatment area) for any individual skin condition prior to the treatment Day baseline sample collection will be excluded from the study and will not be randomized.

Adverse Events (including post treatment skin irritation scores of 3), will also be summarized. Summary tables will present incidence rates of adverse events by treatment group for all subjects who enter the treatment period. Listings of Adverse Events will be provided.

The statistical significance of differences in skin irritation between the Investigational Product, Vehicle Control and Saline Control will be evaluated using Fisher's exact test on skin irritation data summarized as follows: any reaction above zero (no reaction) on the skin irritation rating scale for any category (erythema, edema, rash, and dryness) will be considered a positive signal for that substance. If Fisher's exact test shows there is an overall significant treatment effect, Fisher's exact test or two-proportion test with Score method with multiplicity adjustment on the alpha level may be used for multiple sub-group comparisons to find out which comparisons show the difference. Odds ratio (odds of having positive signals for one treatment / odds of having positive signals for the other treatment) using Fisher's exact test or the difference in percentage of positive signals between treatments using a two-proportion test may be calculated along with the confidence interval for each category at the certain time interval.

Examples for Fisher's exact test and two-proportion test with Score method are shown below.

```
> # overall treatment effect
> irr_tab <- matrix(c(2, 1, 3, 22, 23, 21),
+   nrow = 3,
+   dimnames =
+   list(c("A", "B", "C"),
+        c("Positive (Score > 0)", "Non-positive (Score = 0)")))
> irr_tab
```

	Positive (Score > 0)	Non-positive (Score = 0)
A	2	22
B	1	23
C	3	21

```
> irr <- fisher.test(irr_tab, alternative = "two.sided",
+   conf.level = 0.95)
> print(irr)
```

Fisher's Exact Test for Count Data

```
data: irr_tab
p-value = 0.8654

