alternative hypothesis: two.sided
```

```
> # subgroup comparisons
> library(PropCIs)
> print(diffscoreci(2, 22, 1, 23, conf.level = 0.984))
```

```
data:
98.4 percent confidence interval:
-0.1934747 0.3014313
```

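### For the composite irritation outcome, the alpha adjustment that SAP 7.4.2 adds after a significant three-product test is not needed for error control and makes it harder to name the product

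*SAP*

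**What the plan says.** SAP 7.4.2 (Secondary Analysis) reduces skin irritation to one yes/no outcome per treated site: positive if any of erythema, edema, rash or dryness scores above zero. Differences "between the Investigational Product, Vehicle Control and Saline Control will be evaluated using Fisher's exact test".

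Pairwise work is conditional: "If Fisher's exact test shows there is an overall significant treatment effect", then Fisher's test or a two-proportion score test "with multiplicity adjustment on the alpha level may be used for multiple sub-group comparisons to find out which comparisons show the difference". The text gives neither the adjustment method nor the adjusted level. The only level shown is in the example R code, "print(diffscoreci(2, 22, 1, 23, conf.level = 0.984", whose output is headed "98.4 percent confidence interval". The same paragraph then allows odds ratios or differences, with intervals, to be calculated separately for each irritation category.

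SAP 7.4 sets the general level: "An alpha level of 5% (two-sided) is used for all analyses". Protocol 17.3.2 asks for a follow-up analysis after a significant overall test and mentions no alpha adjustment.

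**The concern.** The composite comparison is protected twice against false positives: once by the overall test, and again by a reduced level for each pair. With exactly three products the first protection is enough, so the second costs sensitivity and returns nothing that is needed.

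This matters because safety is the study's secondary objective and irritation is one of its two measures. The stated purpose of the pairwise step is to find out where the difference lies. Under the illustrated level, the analysis can conclude that the three products differ and then fail to attach that difference to any pair.

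**Working it through.** **Inputs.** Three products and 24 sites per product per body site (SAP 3.3, Table 1); overall level 5% two-sided (SAP 7.4); illustrated pairwise level 1 − 0.984 = 0.016 (SAP 7.4.2). For comparison, 0.05/3 = 0.0167, and 3 × 0.016 = 0.048. The documents give no irritation rates, so rates are assumed below. Groups are treated as independent unless stated.

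**Reproducing the SAP's example.** The table "irr_tab <- matrix(c(2, 1, 3, 22, 23, 21" has 2, 1 and 3 positives out of 24. Full enumeration of the 3×2 exact test gives p = 0.8654, as printed. The score interval for 2/22 against 1/23 at 98.4%, with the N/(N − 1) variance factor, is (−0.1935, 0.3014), also as printed. (22 and 23 are the example's non-positive counts, not its group sizes. That is a separate matter and does not affect this point.)

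**Logic.** Call the pairwise nulls H12, H13 and H23, and the global null H123. Any two pairwise nulls together imply H123, so the closed family is just {H123, H12, H13, H23}. If all products are equal, a pair can be falsely named only if the 5% overall test rejects. If exactly one pair is equal, there is only one true null, and it is tested at 5%. Testing H123 at 5% and then each pair at 5% therefore controls the family-wise error.

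**Exact check.** All 25³ tables were enumerated with independent binomials, and the error maximised over the true rates:

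| Rule after a significant overall test (n = 24) | All three equal | One pair equal |
|---|---|---|
| Fisher pairs at 5% | 4.3% | 2.9% |
| Fisher pairs at 1.6% | 1.9% (same without the overall test) | – |
| Score pairs at 5% | 4.3% | 5.95% |

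The last cell exceeds 5% because the score test is asymptotic, so the strict guarantee holds for Fisher pairs only.

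**What the adjustment costs, by example.** For counts k/0/0 with 24 per product, overall p = 3·C(24,k)/C(72,k) and pairwise Fisher p = 2·C(24,k)/C(48,k).

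- 5/0/0: overall 3 × 42,504 / 13,991,544 = 0.009; pair 2 × 42,504 / 1,712,304 = 0.0496. The score lower limit is −0.010 at 98.4% and +0.054 at 95%. Both methods name the pair at 5% and neither does at 1.6%.
- 7/1/1: overall p = 0.015; pair 0.048; score lower limits −0.015 (98.4%) and +0.044 (95%). Same pattern.
- 6/0/0: overall p = 0.0026; pair 0.022. Fisher at 1.6% names nothing; the score test (p about 0.0096) names the pair even at 1.6%.
- 4/0/0: overall p = 0.031; pair 0.109. Fisher names nothing even at 5%.

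**What it costs on average.** Exact percentages of all trials, at assumed true rates of 30/5/5%; the overall test is significant in 67.6%:

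| Pairwise test | Some pair named at 1.6% | Some pair named at 5% |
|---|---|---|
| Fisher | 41.9% | 64.1% |
| Score | 57% | 68% |

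With Fisher, a significant overall test is left with no pair named in 1 − 41.9/67.6 = 38% of cases at 1.6%, against 1 − 64.1/67.6 = 5% at 5%. At 25/2/2% (overall test significant in 74.0%), Fisher names a pair in 35.2% against 67.2%. At 40/5/5%, the score test does so in 85% against 90%.

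**If abdomen and groin are pooled (48 per product), at 30/5/5%.** The overall test is significant in 95%. Given that, no pair is named at 1.6% in 6% (Fisher) or 1.8% (score), against 0.4% or 0% at 5%.

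**Pairing.** Each subject receives two products. Simulating the 12/12/12 layout with a latent within-subject correlation of 0.5 and equal rates of 10% to 30%, the overall test rejects in 1.7% to 2.4% of trials. Positive correlation makes it more conservative, not less.

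**The case against.** The strongest objection is about the family. A reader might infer that the overall test makes every later irritation comparison safe at 5%. The documents do not support that. SAP 7.4.2 tests a composite and then allows estimates for each of four categories, up to 4 × 3 = 12 pairwise comparisons. One category can produce the significant composite while the other three are true nulls. Take an assumed case with erythema at 60/5/5% and the other categories equal at 10%. Unadjusted 5% tests after a significant composite give at least one false category-level pair in about 10.7% of simulated trials (Fisher) or 26% (score), against 0.9% and 3.7% at 1.6%. This stands, and it limits the point to the composite.

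Three further inferences go too far.

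- That the SAP requires 1.6% per pair. The text says only that adjusted tests may be used; the level appears in example code, beside an overall p of 0.8654 that would not have led to pairwise tests at all.
- That the adjustment contradicts the 5% level in SAP 7.4. A 5% family-wise level split over pairs is compatible with it, and the SAP elsewhere follows an overall ANOVA with Tukey comparisons.
- That an irritating product would go unseen. Any score of 1 or more is reported, and adverse events are tabulated by treatment group. What may be lost is the formal attribution.

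It is also fair to say that the loss is about half as large with the score test as with Fisher at 30/5/5%, that it shrinks with pooling, and that this is an unpowered phase 2 study. None of this gives the extra adjustment a role for composite Fisher pairs.

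**Conclusion.** The point holds for the composite outcome, with three products and pairwise Fisher tests. There the overall 5% test is sufficient, and any further alpha adjustment only reduces the chance of naming the product. At 24 sites per product and assumed rates of 30/5/5%, that chance falls by about 22 percentage points with Fisher (64% to 42%) and about 11 with the score test (68% to 57%).

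The sizes rest on assumed rates, independent groups and the illustrated 1.6% level; the error-control argument does not depend on the assumed rates. It applies within each overall test, so separate tests by body site are separate families. The change reduces but does not abolish unnamed results, as 4/0/0 shows. This is a minor improvement to a secondary safety analysis and does not touch the primary analysis.

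**What to change.** In SAP 7.4.2, replace the adjustment clause with text to this effect: for the composite irritation outcome, within each overall test, a significant three-product Fisher test at 5% is followed by pairwise Fisher's exact tests, each at two-sided 5% with no further adjustment (closed testing, three groups).

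Add that any per-category comparisons keep a multiplicity adjustment, and name its method and family, because the composite test does not protect them.

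Report score intervals descriptively. Either set the confidence level in the example to 0.95 and label the intervals as individual, or keep 0.984 and label them as simultaneous.

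The cost is a few sentences and possibly one code argument; no data collection changes. The statistical price is that individual 95% intervals do not have simultaneous coverage, which is why the label is needed.

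### SAP 7.4.2: the example score interval for skin irritation uses the non-positive counts (22, 23) as sample sizes instead of the arm totals (24, 24)

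*SAP*

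**What the plan says.** SAP 7.4.2 counts any irritation score above zero as a positive signal and compares the three products with an overall Fisher exact test. If that test is significant, pairwise comparisons may follow, by Fisher's test or by a two-proportion score method, with the alpha level adjusted for multiplicity. The quantity attached to the score method is "the difference in percentage of positive signals between treatments using a two-proportion test".

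R code follows, introduced by "Examples for Fisher's exact test and two-proportion test with Score method are shown below". The table is filled by "matrix(c(2, 1, 3, 22, 23, 21". Its first column holds the positive counts (A 2, B 1, C 3) and its second the non-positive counts (A 22, B 23, C 21). The overall Fisher p-value is printed as 0.8654. The A versus B comparison is then "print(diffscoreci(2, 22, 1, 23, conf.level = 0.984", with output labelled "98.4 percent confidence interval" and limits -0.1934747 and 0.3014313.

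**The concern.** A score interval for a difference of two proportions needs, for each arm, the number of positives and the number observed. The second and fourth arguments of the example call are 22 and 23. These are the entries of the non-positive column, not the arm sizes. If they act as denominators, the interval does not estimate the difference in percentages that the text names.

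Using n - x in place of n replaces the proportion x/n by the odds x/(n - x). The two are close when positives are rare and diverge as the rate rises. The pairwise step is reached only after a significant overall test, which needs enough positives in at least one arm for the gap to matter. This is also the only worked specification of the score method in the SAP, so a programmer might well copy it.

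**Working it through.** **Inputs (all from the SAP 7.4.2 example).** Positives: A 2, B 1, C 3. Non-positives: A 22, B 23, C 21. Arm totals: 2 + 22 = 24, 1 + 23 = 24, 3 + 21 = 24. Confidence level: 0.984.

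**Formula.** For a trial difference δ, with observed proportions p1 = x1/n1 and p2 = x2/n2 and N = n1 + n2:

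z²(δ) = (p1 - p2 - δ)² / { [q1(1 - q1)/n1 + q2(1 - q2)/n2] × N/(N - 1) }

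Here q1 and q2 are the maximum-likelihood proportions under q1 - q2 = δ. The limits are the two values of δ at which z²(δ) equals the 0.984 quantile of chi-square on 1 degree of freedom, 5.803.

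**Step 1: reproduce the SAP's figure, then use the arm totals.**

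| Denominators | Proportions | Difference | 98.4% interval | Width |
|---|---|---|---|---|
| 22 and 23 (as in the call) | 9.09%, 4.35% | 0.0474 | (-0.1934747, 0.3014313) | 0.495 |
| 24 and 24 (arm totals) | 8.33%, 4.17% | 0.0417 | (-0.1899366, 0.2803334) | 0.470 |

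The first row matches the printed output to seven decimals, so 22 and 23 did act as sample sizes. The documents do not state the function's argument order, but the match settles it and also rules out a text-extraction error. Other interval types with denominators 22 and 23 do not match: without the N/(N - 1) factor (-0.1899, 0.2980), Newcombe (-0.1855, 0.2924), Wald (-0.1323, 0.2271). No variant tried with 24 and 24 matches.

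**Step 2: check the neighbouring example.** Fisher's exact test on the 3 × 2 table with row totals of 24 gives p = 0.8654, as printed. That test correctly treats 22, 23 and 21 as non-positive counts.

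**Step 3: size of the error in the example.** Upper limit: 0.3014 - 0.2803 = 0.021 too high. Lower limit: 0.1935 - 0.1899 = 0.0035 too low. Both intervals include 0.

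**Step 4: what reuse could do.** The documents give no expected irritation rate. The counts below are assumptions, with 24 per arm taken from the example.

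| Positives of 24 in the three arms | Overall Fisher p | Pair | Interval with n = 24 | Interval with n - x |
|---|---|---|---|---|
| 8, 2, 1 | 0.0215 | 8 vs 2 | (-0.040, 0.517) | 8/16 vs 2/22: (0.058, 0.697) |
| 5, 0, 0 | 0.0091 | 5 vs 0 | (-0.010, 0.456) | 5/19 vs 0/24: (0.036, 0.542) |

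In both cases the copied pattern excludes 0 and the stated target does not. For 8 versus 2, pairwise Fisher gives p = 0.072. That reversal also holds at the Bonferroni level for three comparisons, 1 - 0.05/3 = 98.33%: (-0.038, 0.515) against (0.060, 0.696). It does not hold at an unadjusted 95%, where the interval with n = 24 is (0.020, 0.470) and already excludes 0. The SAP, however, calls for a multiplicity adjustment.

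**Step 5: direction.** There are 364 unordered patterns of 0 to 11 positives of 24 in three arms, and 138 of them have an overall Fisher p below 0.05. Those 138 contain 377 pairs with unequal counts. In 76 of these pairs, spread over 60 patterns, the copied pattern excludes 0 and the interval with n = 24 does not. The reverse never occurs. These are counts of possible tables, not probabilities.

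**The case against.** The error is in an illustration with invented counts, and the text beside it states the target correctly, so an analyst who follows the text will use arm totals. The step is optional and conditional: it needs a significant overall test, Fisher's test is an equal alternative, and the example itself (p = 0.8654) would never reach it. No acceptance criterion depends on it, since SAP Table 2 lists efficacy standards only. Nothing in the documents shows that a production program was built from this line. All of that stands, and it limits the weight of the point.

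Reversals are also confined to tables with appreciable irritation. None occurs when every arm has at most 4 positives of 24, only 3 patterns show one when every arm has at most 5, and 44 of the 60 patterns have an arm with 9 or more. This stands too, and without an expected rate nobody can say how likely such tables are.

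Finally, the interval with arm totals treats the arms as independent, although SAP 3.3 has 12 of the 36 subjects receiving both A and B. It is therefore right as an execution of the SAP's named method, not as a validated inference for this paired design. That qualification is fair, but it does not rescue the denominators 22 and 23.

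**Conclusion.** The point holds and is minor. The example call contradicts the table above it and the target stated in the same section. The finding rests on the SAP's own counts and on an exact match to its printed output.

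The effect on the example is small and changes no reading. The potential effect on trial data is one-sided, towards declaring an irritation difference between products that the stated target does not support. It arises only if the score method is chosen and the call is copied. The sizes given for that case assume 24 observations per arm, a 98.4% level and hypothetical counts. The number of observations in the safety analysis may differ, because safety uses all randomized subjects.

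**What to change.** Change the example call to `diffscoreci(2, 24, 1, 24, conf.level = 0.984)`, preferably taking the denominators from `rowSums(irr_tab)` so that the code cannot drift from the table. Replace the printed limits with (-0.1899366, 0.2803334). Check any analysis program that reuses the line.

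The cost is one line of example code, one line of output and that check. Design, data collection and the primary analysis do not change.

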7.4.3 Exploratory Analyses

7.4.3.1 Log Reduction

Log₁₀ reductions will be compared between test materials by an Analysis of Variance (ANOVA) for each body site based on mITT data and/or per-protocol data. In the ANOVA model, the response is the log₁₀ reduction and the predictor is the treatment as a fixed effect. The average difference in log reduction between treatments at 10 minutes post-treatment time point will be estimated. However, all conclusions for the average treatment effect will be based on the primary analysis only.

An example for results of comparisons above can be found in Tables 9.

Table 9: Example: Log reduction comparisons for Groin

Comparison	N Pairs	Difference	Conf Int
IP Baseline-IP 10 min vs. VC Baseline-VC 10 min	24	0.13	-0.44, 0.70
IP Baseline-IP 10 min vs. SC Baseline-SC 10 min	24	0.11	-0.65, 0.87

7.4.3.2 Product Expression Volumes/Weight

An analysis of variance (ANOVA) of the applied volumes/weight will be performed separately for each body site based on mITT data and/or per-protocol data. In the model, there will be a random subject effect, a fixed body side (left or right) effect, a fixed treatment effect and the interaction between fixed effects. ANOVA table will be checked to see whether the treatment has a significant effect on product expression volumes as well as the interaction. If a significant difference is found, subgroup comparisons with Tukey's method will be made to determine which pair of comparisons shows significant difference.

7.5 Graphs

7.5.1 Average Treatment Effect Per Primary Analysis

Graphs for least squares means with 95% intervals estimated from the regression model for each treatment will be provided (see an examples in Figure 1).

Graphs for the average treatment effect between IP vs. VC/SC with 95% intervals (as in Table 8) will be provided (see an example in Figure 2).

Groin

[figure not shown]

Figure 1: Mean with confidence interval plots for log reduction for Groin

Example: Average Treatment Effect for IP vs. VC and SC for Groin

[figure not shown]

Figure 2: Average difference between products in log reduction from baseline for Groin

8 Appendix

Subjects not passing the treatment-day baseline criteria will be listed.

Subjects included in mITT analysis, but excluded from per-protocol analysis, if any, will be listed.

9 References

References

- [1] Alex Dmitrienko, Ajit C.Tamhane, Frank Bretz Multiple Testing Problems in Pharmaceutical Statistics

Signature Page for MPS-17IPVAW10_Statistical_Analysis_Plan

Approved	[name] Statistician, Corporate/Shared Services Statistician 23-Jun-2017 13:40:59 GMT+0000
----------	---

Approved	[name] Manager Statistics, Corporate/Shared Services Functional Management 26-Jun-2017 12:56:35 GMT+0000
----------	---

Approved	[name] Study Manager 29-Jun-2017 22:17:31 GMT+0000
----------	---

Signature Page for MPS-17IPVAW10_Statistical_Analysis_Plan - System Version No.
